4.1.7 Organ Function Requirements

4.1.7.1 Adequate Bone Marrow Function Defined as:

- a. For patients with solid tumors without known bone marrow involvement:
 - Peripheral absolute neutrophil count (ANC) $\geq 1000/\text{mm}^3$
 - Platelet count $\geq 100,000/\text{mm}^3$ (transfusion independent, defined as not receiving platelet transfusions for at least 7 days prior to enrollment)
- b. Patients with known bone marrow metastatic disease will be eligible for study provided they meet the blood counts in Section

[4.1.7.1.a](#) (may receive transfusions provided they are not known to be refractory to red cell or platelet transfusions). These patients will not be evaluable for hematologic toxicity.

4.1.7.2 Adequate Renal Function Defined as:

- Creatinine clearance or radioisotope GFR $\geq 70\text{ml/min}/1.73\text{ m}^2$ or
- A serum creatinine based on age/gender as follows:

Age	Maximum Serum Creatinine (mg/dL)	
	Male	Female
1 to < 2 years	0.6	0.6
2 to < 6 years	0.8	0.8
6 to < 10 years	1	1
10 to < 13 years	1.2	1.2
13 to < 16 years	1.5	1.4
≥ 16 years	1.7	1.4

The threshold creatinine values in this Table were derived from the Schwartz formula for estimating GFR (Schwartz et al. J. Peds, 106:522, 1985) utilizing child length and stature data published by the CDC.

4.1.7.3 Adequate Liver Function Defined as:

- Bilirubin (sum of conjugated + unconjugated) $\leq 1.5 \times$ upper limit of normal (ULN) for age
- SGPT (ALT) ≤ 135 U/L. (For the purpose of this study, the ULN for SGPT is 45 U/L.)
- Serum albumin ≥ 2 g/dL.

4.1.7.4 Adequate Cardiac Function Defined As:

- Shortening fraction of $\geq 27\%$ by echocardiogram, or
- Ejection fraction of $\geq 50\%$ by gated radionuclide study.
- QTc interval ≤ 480 milliseconds

4.1.8 Patients must be able to swallow intact capsules.

4.1.9 Informed Consent: All patients and/or their parents or legally authorized representatives must sign a written informed consent. Assent, when appropriate, will be obtained according to institutional guidelines.

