5.4.1 Non-Hematological Dose-Limiting Toxicity

5.4.1.1 Any Grade 3 or greater non-hematological toxicity attributable to the investigational drug with the specific exclusion of:

- Grade 3 nausea and vomiting of less < 3 days duration
- Grade 3 liver enzyme elevation, including ALT/AST/GGT that returns to levels that meet initial eligibility criteria or baseline within 7 days. See [Appendix XI](#) for values that represent thresholds between CTCAE grades.

Note: For the purposes of this study the ULN for ALT is defined as 45 U/L regardless of baseline.

- Grade 3 or 4 fever < 5 days duration.
- Grade 3 infection < 5 days duration.
- Grade 3 hypophosphatemia, hypokalemia, hypocalcemia or hypomagnesemia responsive to supplementation.

- Any Grade 2 visual disturbance that persists for ≥ 1 week.
- Any Grade 2 non-hematological toxicity that persists for ≥ 7 days and is considered sufficiently medically significant or sufficiently intolerable by patients that it requires treatment interruption.
- Note: Allergic reactions that necessitate discontinuation of study drug will not be considered a dose-limiting toxicity.

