7.5.3 BVD-523FB (ulixertinib) is a P-glycoprotein (P-gp) transporter substrate, and is highly protein bound (99-100% protein binding). Use caution in patients who are also receiving strong P-gp inhibitors (eg., amiodarone, carvedilol, clarithromycin, dronedarone, itraconazole, lapatinib, lopinavir and ritonavir, propafenone, quinidine, ranolazine, ritonavir, saquinavir and ritonavir, telaprevir, tipranavir and ritonavir, verapamil) or highly protein-bound drugs with narrow therapeutic ranges.

8.0 **EVALUATIONS/MATERIAL AND DATA TO BE ACCESSIONED**

8.1 **Required Clinical, Laboratory and Disease Evaluation**

All clinical and laboratory studies to determine eligibility must be performed within 7 days prior to enrollment unless otherwise indicated. Laboratory values used to assess eligibility (see [Section 4.0](#)) must be no older than seven (7) days at the start of therapy. Laboratory tests need **not** be repeated if therapy starts **within** seven (7) days of obtaining labs to assess eligibility. If a post-enrollment lab value is outside the limits of eligibility, or laboratory values are older than 7 days, then the following laboratory evaluations must be re-checked within 48 hours prior to initiating therapy: CBC with differential, bilirubin, ALT (SGPT) and serum creatinine. If the recheck is outside the limits of eligibility, the patient may not receive protocol therapy and will be considered off protocol therapy. Imaging studies, bone marrow aspirate and/or biopsy, must be obtained within 14 days prior to start of protocol therapy (repeat the tumor imaging if necessary).

STUDIES TO BE OBTAINED	Pre-Study	During Cycle 1	Prior to Subsequent Cycles [^]
History	X	Weekly	X
Physical Exam with vital signs	X	Weekly	X
Neurologic Exam	X		
Height, weight, BSA	X		X
Performance Status	X		
Pregnancy Test ¹	X		
CBC, differential, platelets	X	Twice Weekly (every 3 to 4 days) ^{2,3}	Weekly ^{2,3}
Urinalysis	X		
Electrolytes including Ca ⁺⁺ , PO ₄ , Mg ⁺⁺	X	Weekly	X
Creatinine, ALT, bilirubin	X	Weekly	X
Albumin	X		X
ECHO or gated radionuclide study	X		Every 3 cycles
EKG	X	End of Cycle 1	
Ophthalmologic Exam ¹⁰	X		
Tumor Disease Evaluation ^{4-A, 4-B, 4-C}	X		Every other Cycle x 3 then q 3 Cycles ⁴
Plain radiograph tibial growth plate (bone x-ray tests) ¹¹	X		Prior to Cycles 2 and 5, then every 6 months
Bone Marrow Aspirate and/or biopsy ^{5,6}	X ⁶		
Medication Diary ⁷		Weekly	X
Pharmacokinetics (optional) ⁸		X	

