Nausea			Nausea (Gr 2)
	Vomiting		Vomiting (Gr 2)
GENERAL DISORDERS AND ADMINISTRATION SITE CONDITIONS			
	Chills		Chills (Gr 2)

Adverse Events with Possible Relationship to BVD-523FB (ulixertinib) (CTCAE 5.0 Term) [n= 208]			Specific Protocol Exceptions to Expedited Reporting (SPEER)
Likely (>20%)	Less Likely (<=20%)	Rare but Serious (<3%)	
Fatigue	Edema limbs	Edema face	Edema limbs (Gr 2)
	Fever		Fatigue (Gr 2)
	Non-cardiac chest pain		Fever (Gr 2)
	Pain		Non-cardiac chest pain (Gr 2)
INFECTIONS AND INFESTATIONS			Pain (Gr 2)
	Infection ⁴		Infection⁴ (Gr 2)
INVESTIGATIONS			
	Alanine aminotransferase increased		Alanine aminotransferase increased (Gr 2)
	Alkaline phosphatase increased		Alkaline phosphatase increased (Gr 2)
	Aspartate aminotransferase increased		Aspartate aminotransferase increased (Gr 2)
	Blood bilirubin increased		Blood bilirubin increased (Gr 2)
	Creatinine increased		Creatinine increased (Gr 2)
		Electrocardiogram QT corrected interval prolonged	
	Lymphocyte count decreased		Lymphocyte count decreased (Gr 2)
	Neutrophil count decreased		Neutrophil count decreased (Gr 2)
METABOLISM AND NUTRITION DISORDERS			
	Anorexia		Anorexia (Gr 2)
	Dehydration		Dehydration (Gr 2)
	Hyperglycemia		Hyperglycemia (Gr 2)
	Hyperphosphatemia		Hyperphosphatemia (Gr 2)
	Hypoalbuminemia		Hypoalbuminemia (Gr 2)
	Hypocalcemia		Hypocalcemia (Gr 2)
	Hypokalemia		Hypokalemia (Gr 2)
	Hypomagnesemia		Hypomagnesemia (Gr 2)
	Hyponatremia		Hyponatremia (Gr 2)
MUSCULOSKELETAL AND CONNECTIVE TISSUE DISORDERS			
	Arthralgia		Arthralgia (Gr 2)
	Generalized muscle weakness		Generalized muscle weakness (Gr 2)
	Musculoskeletal and connective tissue disorder – Other (muscle twitch)		Musculoskeletal and connective tissue disorders – Other (muscle twitch) (Gr 2)
	Myalgia		Myalgia (Gr 2)
NEOPLASMS BENIGN, MALIGNANT AND UNSPECIFIED (INCL CYSTS AND POLYPS)			
		Neoplasms benign, malignant and unspecified (incl cysts and polyps) - Other (squamous cell carcinoma, keratoacanthoma-type, mid forehead)	
NERVOUS SYSTEM DISORDERS			
	Dizziness		Dizziness (Gr 2)
	Dysgeusia		Dysgeusia (Gr 2)

Adverse Events with Possible Relationship to BVD-523FB (ulixertinib) (CTCAE 5.0 Term) [n= 208]			Specific Protocol Exceptions to Expedited Reporting (SPEER)

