The rolling six phase 1 trial design²⁸ will be used for the conduct of this study. Two to six patients can be concurrently enrolled onto a dose level, dependent upon (1) the number of patients enrolled at the current dose level, (2) the number of patients who have experienced DLT at the current dose level, and (3) the number of patients entered but with tolerability data pending at the current dose level. Accrual is suspended when a cohort of six has enrolled or when the study endpoints have been met.

Dose level assignment is based on the number of participants currently enrolled in the cohort, the number of DLTs observed, and the number of participants at risk for developing a DLT (i.e., participants enrolled but who are not yet assessable for toxicity). For example, when three participants are enrolled onto a dose cohort, if toxicity data is available for all three when the fourth participant entered and there are no DLTs, the dose is escalated and the fourth participant is enrolled to the subsequent dose level. If data is not yet available for one or more of the first three participants and no DLT has been observed, or if one DLT has been observed, the new participant is entered at the same dose level. Lastly, if two or more DLTs have been observed, the dose level is de-escalated. This process is repeated for participants five and six. In place of suspending accrual after every three participants, accrual is only suspended when a cohort of six is filled. When participants are inevaluable for toxicity, they are replaced with the next available participant if escalation or de-escalation rules have not been fulfilled at the time the next available participant is enrolled onto the study.

The following table provides the decision rules for enrolling a patient at (i) the current dose level (ii) at an escalated dose level, (iii) at a de-escalated dose level, or whether the study is suspended to accrual:

# Pts Enrolled	# Pts with DLT	# Pts without DLT	# Pts with Data Pending	Decision
2	0 or 1	0, 1 or 2	0, 1 or 2	Same dose level
2	2	0	0	De-escalate*
3	0	0, 1 or 2	1, 2 or 3	Same dose level
3	1	0, 1 or 2	0, 1 or 2	Same dose level
3	0	3	0	Escalate**
3	≥ 2	0 or 1	0 or 1	De-escalate*
4	0	0, 1, 2 or 3	1, 2, 3 or 4	Same dose level
4	1	0, 1, 2 or 3	0, 1, 2 or 3	Same dose level
4	0	4	0	Escalate**
4	≥ 2	0, 1 or 2	0, 1 or 2	De-escalate*
5	0	0, 1, 2, 3 or 4	1, 2, 3, 4 or 5	Same dose level
5	1	0, 1, 2, 3 or 4	0, 1, 2, 3 or 4	Same dose level
5	0	5	0	Escalate**

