All eligible patients who receive at least one dose of protocol therapy will be considered in the evaluation of toxicity. In addition, for the dose-escalation portion during Cycle 1, patients without DLT must receive at least 85% of the prescribed dose per protocol guidelines and must have the appropriate toxicity monitoring studies performed to be considered evaluable for toxicity for the purpose of determining dose escalation and defining the recommended phase 2 dose. Patients under [Section 4.1.7](#) are not evaluable for DLT if they do not experience a non-hematologic DLT.

11.7 **Progression free survival (PFS)**

Progression free survival will be defined as time from the initiation of protocol treatment to the occurrence of any of the following events: disease progression or disease recurrence or death from any cause. All patients surviving at the time of analyses without events will be censored at their last follow-up date.

PFS along with the confidence intervals will be estimated using the Kaplan-Meier method. Patients with local calls of disease progression (i.e. calls made by the treating institution), will be counted as having had an event, even if the central review does not declare progression. We will also report PFS based on central radiology review as a secondary analysis, if adequate number of disagreements in progressions exist between the treating institutions and the central radiology review to make such an analysis meaningful.

11.8 **Correlative Studies**

A descriptive analysis of pharmacokinetic (PK) parameters will be performed to define systemic exposure, drug clearance, and other pharmacokinetic parameters. The PK

parameters will be summarized with simple summary statistics, including means, medians, ranges, and standard deviations (if numbers and distribution permit).

A descriptive analysis of the exploratory aims described in [Section 1.3](#) will be performed and will be summarized with simple summary statistics. All of these analyses will be descriptive in nature.

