13.4 Definition of Onset and Resolution of Adverse Events

Note: These guidelines below are for reporting adverse events on the COG case report forms and do not alter the guidelines for CTEP-AERS reporting.

- 13.4.1 If an adverse event occurs more than once in a course (cycle) of therapy only the most severe grade of the event should be reported.
- 13.4.2 If an adverse event progresses through several grades during one course of therapy, only the most severe grade should be reported.
- 13.4.3 The duration of the AE is defined as the duration of the highest (most severe) grade of the Adverse Effects.
- 13.4.4 The resolution date of the AE is defined as the date at which the AE returns to baseline or less than or equal to Grade 1, whichever level is higher (note that the resolution date may therefore be different from the date at which the grade of the AE decreased from its highest grade). If the AE does not return to baseline the resolution date should be recorded as "ongoing."
- 13.4.5 An adverse event that persists from one course to another should only be reported once unless the grade becomes more severe in a subsequent course. An adverse event which resolves and then recurs during a different course, must be reported each course it recurs.

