a.	History/Physical Exam (including VS).
b.	Ht/Wt/BSA
c.	CBC/differential/platelets- If patients have Grade 4 neutropenia then CBCs should be checked at least every other day until recovery to Grade 3 or until meeting the criteria for dose limiting toxicity. If patients develop Grade 3 or greater thrombocytopenia then CBCs should be checked every 3 to 4 days until recovery per Section 6.1 .
d.	Electrolytes including Ca++, PO4, Mg++
e.	Creatinine, ALT, bilirubin
f.	Medication Diary- (see Appendix III) should be reviewed after completion of each treatment cycle and uploaded into RAVE. The medication diary should be collected weekly.
g.	Pharmacokinetics- see Section 8.4 for details of PK studies.
h.	EKG For information related to prestudy observations please refer to section 8.1
i.	Plain radiograph tibial growth plate (bone x-ray tests) - Plain radiographs of at least one tibial growth plate should be obtained in all patients prior to first dose of protocol therapy and prior to cycle 2.
j.	Albumin

This listing only includes evaluations necessary to answer the primary and secondary aims. OBTAIN OTHER STUDIES AS REQUIRED FOR GOOD CLINICAL CARE.

Comments

(Include any held doses, or dose modifications)

All Subsequent Cycles

Therapy Delivery Map – All Subsequent Cycles	Patient COG ID number Accession number
--	---

Criteria to start each cycle are listed in [Section 5.2](#). Extensive treatment details are in [Section 5.1](#).

DRUG	ROUTE	DOSAGE	DAYS	IMPORTANT NOTES
BVD-523FB (ulixertinib) IND # 134661	PO	Dose Level -1: 175 mg/m ² /dose BID (max 300 mg BID) Dose Level 1: 260 mg/m ² /dose BID (max 450 mg BID) Dose Level 2: 350 mg/m ² /dose BID (max 600 mg BID)	1-28	Refer to dosing nomogram (Appendix V) Take by mouth on an empty stomach either 1 hour before a meal or 2 hours after a meal. Capsules should not be opened, crushed or chewed. If a patient misses or vomits a dose, an additional dose should not be taken. Patients should resume dosing at the next scheduled time. If capsule is broken and the powder of the capsules gets on skin, wash the exposed area with as much water as necessary.

Enter Cycle #: _____ Ht _____ cm Wt _____ kg BSA _____ m²

Date Due	Date Given	Day	BVD-523FB (ulixertinib) mg AM mg PM	Studies
			Enter calculated dose above as per dosing nomogram and actual dose administered below	
		1	mg AM mg PM	a-f, j
		2	mg AM mg PM	
		3	mg AM mg PM	
		4	mg AM mg PM	
		5	mg AM mg PM	
		6	mg AM mg PM	
		7	mg AM mg PM	
		8	mg AM mg PM	c
		9	mg AM mg PM	

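### Grade 3 AST counts toward dose-limiting toxicity, but the plan schedules no AST test and sets no AST entry limit, so an isolated AST event can go unseen in Cycle 1

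*Combined protocol and SAP*

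**What the plan says.** Section 5.4.1.1 treats a non-hematological toxicity of Grade 3 or above that is attributed to ulixertinib as a DLT, apart from listed exclusions. One exclusion is "Grade 3 liver enzyme elevation, including ALT/AST/GGT that returns to levels that meet initial eligibility criteria or baseline within 7 days". Section 6.2 uses the same pair of comparators, eligibility level or baseline, to decide within 14 days whether a child resumes at a reduced dose or comes off therapy.

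The liver entry criteria in Section 4.1.7.3 cover bilirubin, ALT (at most 135 U/L) and albumin. For ALT the reference is fixed: "For the purpose of this study, the ULN for SGPT is 45 U/L". There is no AST criterion. The Section 8.1 schedule lists "Creatinine, ALT, bilirubin" pre-study, weekly in Cycle 1 and before later cycles, and item e in both Appendix VI maps repeats it. The pre-treatment re-check list in Sections 4.0 and 8.1 also names ALT but not AST.

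AST does appear elsewhere. Section 2.3.1 lists it among the adult DLTs. Section 9.1.9 lists "Aspartate aminotransferase increased" in the column for events seen in 20% of patients or fewer. Appendix XI gives AST grade cut-offs from a fixed upper limit of normal (ULN) of 50 U/L.

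**The concern.** The DLT definition relies on a laboratory value that the schedule never asks for. For a child without DLT to count in dose finding, Section 11.6 requires at least 85% of the prescribed dose and that the child "must have the appropriate toxicity monitoring studies performed to be considered evaluable for toxicity". The natural reading of that phrase is the Section 8.1 schedule. A child with a full set of scheduled tests and no AST would then count as evaluable and DLT-free, even if AST had reached Grade 3.

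Section 2.4.1 reports no earlier studies of the drug in children, and dose finding runs on cohorts of at most six. Under the rolling six rule in Section 11.2.2, "if toxicity data is available for all three when the fourth participant entered and there are no DLTs, the dose is escalated". Completeness of DLT detection therefore matters. AST was named as dose-limiting in adults, while the enzyme that is scheduled, ALT, was not. The Section 6.2 decision to resume or stop drug has the same dependence for the individual child.

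**Working it through.** **1. What the plan supplies for each enzyme**

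| Element | ALT | AST |
|---|---|---|
| Named in the DLT exclusion (5.4.1.1) | yes | yes |
| Entry limit (4.1.7.3) | 135 U/L | none |
| Pre-treatment re-check (4.0, 8.1) | yes | no |
| Scheduled test (8.1; Appendix VI item e, both maps) | yes | no |
| Grade cut-offs (Appendix XI) | yes | yes |
| Listed adult DLT (2.3.1) | no | yes |

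**2. Scheduled values through the end of Cycle 1.** ALT: one pre-study, plus item e on days 8, 15, 22 and 28/1, so 1 + 4 = 5. AST: 0.

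**3. Is the grading usable?** The Appendix XI upper bounds for Grades 1, 2 and 3 are 135, 225 and 900 U/L for ALT, which are 3, 5 and 20 times 45. For AST they are 150, 250 and 1000 U/L, which are 3, 5 and 20 times 50. So AST can be graded once it is measured. What is missing is the measurement, a required baseline and an eligibility level to return to.

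**4. An isolated, drug-related Grade 3 AST rise (251 to 1000 U/L) in Cycle 1**

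- *AST never drawn.* The event is unseen and the child can count as DLT-free.
- *AST drawn on site initiative, no baseline.* The general rule makes it a DLT. The exclusion cannot be shown, because there is no eligibility level and no baseline. It counts as a DLT even if it was transient.
- *AST drawn, baseline 50 U/L, day-7 value 120 U/L.* AST has not returned to baseline, so this is a DLT. An ALT of 120 U/L on the same day would be exempt, because it is below 135.

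The error thus has two directions. Without a test, a DLT can be missed. With a test but no baseline, a DLT can be over-called, which is the safer direction.

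**5. Effect on the dose rule.** Section 5.1.1 escalates with fewer than 2 DLTs in the first 6 toxicity-evaluable children. The Section 11.2.2 table agrees at six: 0 or 1 DLT escalates, and 2 or more de-escalates. With three to five fully assessed children, 0 DLTs escalates and 1 keeps the same level. Moving from 0 to 1 therefore changes how many children are enrolled at a level and how soon the next opens. The dose decision differs only if the count in a cohort of up to six moves between 1 and 2 or more.

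**6. How often?** The only AST frequency is the Section 9.1.9 band of 20% or less among 208 patients, not split by grade. If children match it (an assumption), at most 0.20 × 6 = 1.2 of six would have any AST rise. The Grade 3 share, and the share without a qualifying ALT rise, are not given.

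**7. Sensitivity, with assumed rates only.** With six children and counted DLT probability p, P(fewer than 2) = (1 − p)^6 + 6p(1 − p)^5.

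- p = 0.30: 0.118 + 0.303 = 0.420
- p = 0.25: 0.178 + 0.356 = 0.534
- p = 0.20: 0.262 + 0.393 = 0.655

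If the true rate were 30%, missing none, 5 or 10 percentage points would give a pass probability of 0.42, 0.53 or 0.66. Nothing in the documents indicates which of these shifts, if any, would apply.

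**The case against.** The strongest reply is that little would actually be lost. ALT is drawn weekly in Cycle 1, and a Grade 3 ALT rise prompts the same DLT assessment. A Grade 3 AST rise that settles to baseline within 7 days is exempt anyway. Suspected DLTs go to the Study Chair within 24 hours (Section 5.3), and evaluations are reviewed weekly (Section 14.4.2). Many sites may draw AST regardless. The adult AST DLT is reported without a dose, and adult escalation ran to 900 mg twice daily against a cap of 600 mg here.

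Most of this stands, and it narrows the point to AST events that are isolated, drug-related and not recovered within 7 days. It does not remove the point. The plan treats AST as a DLT trigger in its own right, and oversight cannot supply a baseline or a day-7 value that was never drawn. Two other clauses do not help. Appendix VI says "This listing only includes evaluations necessary to answer the primary and secondary aims. OBTAIN OTHER STUDIES AS REQUIRED FOR GOOD CLINICAL CARE", which requires no AST and presents the listing as sufficient for the secondary aims, tolerability among them. Section 13.4.4 places resolution at "the date at which the AE returns to baseline or less than or equal to Grade 1, whichever level is higher", but its note confines it to case report forms. Section 10.1 borrows it only for follow-up after removal in Cycle 1.

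A reader might also infer that, with no AST limit, the eligibility limb is met automatically and every Grade 3 AST rise is exempt. The text does not support that. It would empty the requirement to return to a level within 7 days of meaning. Nor is an event without a baseline undecidable: an exclusion that cannot be shown leaves the general rule in force.

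**Conclusion.** The gap is real and modest. A site that follows the plan exactly measures no AST, so one toxicity that the plan defines as dose-limiting can be missed in Cycle 1 in a child who still counts as evaluable. The baseline limb of Sections 5.4.1.1 and 6.2 also has no required AST value.

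A reader might infer that one unseen AST event would send the trial to the wrong dose, or that the chance of escalating is materially inflated. The documents support neither. One DLT in six still allows escalation, and the pass probabilities above rest on assumed rates. The size of the effect on dose decisions cannot be determined.

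This conclusion assumes that the adequate toxicity monitoring required by Section 11.6 means the Section 8.1 schedule, and that no AST requirement sits outside the supplied text. No supplied section points to one. GGT shares the gap: it is named in the exclusion but has no entry limit and no scheduled test.

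**What to change.** Add AST to the liver chemistry row in Section 8.1 and to item e in both Appendix VI maps, so that it covers creatinine, ALT, AST and bilirubin at the existing time points: pre-study, weekly in Cycle 1 and before later cycles. This gives every child a baseline, which makes the existing baseline limb usable for AST, and puts AST on the same weekly footing as ALT in Cycle 1.

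The cost is a short amendment and one more assay on samples already drawn, with no added visits or draws. Through the end of Cycle 1 that is 5 per child: 5 × 12 = 60 for the planned dose-finding children, plus 5 for each replacement, and at most 5 × 49 = 245 for the maximum enrollment. Later pre-cycle samples add one each.

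An explicit AST recovery level is a separate, optional choice for the study team. A level of 150 U/L (3 × ULN, and the top of Grade 1) would parallel ALT, whose 135 U/L is also 3 × ULN. It would loosen the exemption for children with low baseline AST, for example from 25 or 50 U/L to 150 U/L, during first pediatric dose finding. That trade-off should be decided openly, and closing the measurement gap does not depend on it. GGT testing need not be made mandatory.
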